Data Analysis for Drug Repurposing for Effective Alzheimer's Medicines – Montelukast vs Fluticasone

NCT05457855

July 10, 2023

1. Comparison Details

a. Intended aim(s)

To evaluate the comparative risk of dementia onset between patients treated with Montelukast versus Fluticasone for asthma.

b. Primary endpoint

Incident dementia (i.e., Alzheimer's disease, vascular dementia, senile, presenile, or unspecified dementia, or dementia in other diseases classified elsewhere).

[figure not shown]
2. Person responsible for implementation

[figure not shown]
[name]

3. Data Source(s)

Medicare, 2008-2018

4. Study Design Diagrams

5. Cohort Identification

a. Cohort Summary

This study will employ a new user, active comparator, observational cohort study design comparing Montelukast versus Fluticasone. The patients will be required to have continuous enrollment during the baseline period of 365 days before initiation of study drugs (cohort entry/index date). Follow-up for the outcome (dementia) differs between analyses. Follow-up begins the day after drug initiation (analysis 1, 3, 4); 180 days after drug initiation (analysis 2).

b. Key details regarding cohort creation

Index date:

- Day of initiation of new Montelukast versus Fluticasone use

Inclusion criteria for analyses 1, 3, 4:

- Aged \geq 65 years on the index date
- 365 days enrollment in Medicare Parts A, B, and D with no HMO coverage
- No use of Montelukast versus Fluticasone, any time prior to index date (all available lookback approach with a minimum of 365 days)
- No diagnosis of dementia any time prior to and including index date
- No history of nursing home admission recorded in any time prior to and including index date
- At least two claims with asthma diagnosis recorded in 365 days prior to index date (ICD-9 493.0x, 493.1, 493.2x, 493.8x, 493.9x or ICD-10 J44.0, J44.1, J44.9, J45.2x, J45.3x, J45.4x, J45.5x, J45.9x)

Inclusion criteria for analysis 2:

- Aged \geq 65 years on the index date
- 365 days enrollment in Medicare Parts A, B, and D with no HMO coverage or 365 days registration with a practice contributing data to CPRD prior to index date
- No use of Montelukast versus Fluticasone, any time prior to index date (all available lookback approach with a minimum of 365 days)
- No diagnosis of dementia any time prior to and including index date
- No history of nursing home admission recorded in any time prior to and including index date
- At least two claims with asthma diagnosis recorded in 365 days prior to index date (ICD-9 493.0x, 493.1, 493.2x, 493.8x, 493.9x or ICD-10 J44.0, J44.1, J44.9, J45.2x, J45.3x, J45.4x, J45.5x, J45.9x)

DREAM study protocol - Comparison 10 Montelukast vs Fluticasone

493.2x, 493.8x, 493.9x or ICD-10 J44.0, J44.1, J44.9, J45.2x, J45.3x, J45.4x, J45.5x, J45.9x)

- 180-day continuous use of Montelukast versus Fluticasone starting on the index date

c. Flowchart of the study cohort assembly

	Less Excluded Patients	Remaining Patients
All patients		23,466,175
Did not meet cohort entry criteria	-21,749,739	1,716,436
Excluded due to insufficient enrollment	-1,010,844	705,592
Excluded based on Dementia Exclusion	-113,159	592,433
Excluded based on Nursing Home Admission	-62,588	529,845
Excluded based on Peripheral artery disease		
Diagnosis	-454,167	75,678
Excluded anyone aged <65 at index	-24,145	51,533
Patients in Montelukast group		12,575
Patients in Fluticasone group		38,958
Final cohort		51,533

6. Variables

a. Exposure-related variables:

Study drug:

The study exposure of interest is initiation of Montelukast

Comparator:

Fluticasone

b. Covariates:

Demographics	
Age	Region
Gender	Calendar year of index date
Race	Low income subsidy

Dementia risk factors	
Diabetes	Depression
Obesity	Anxiety
Hypertension	Bipolar disorder
Coronary artery disease	Schizophrenia

Markers for healthy behavior, frailty, healthcare use	
Smoking	Number of outpatient visits
Mammography	Number of hospitalizations
Colonoscopy	Number of serum creatinine tests ordered
Fecal occult blood test	Composite frailty score
Influenza vaccination	Number of C-reactive protein tests ordered
Pneumococcal vaccination	Osteoporosis
Herpes zoster vaccination	Fractures
Bone mineral density test	Falls

DREAM study protocol - Comparison 10 Montelukast vs Fluticasone

Number of distinct generic agents	Use of supplemental oxygen
Number of emergency room visits	Combined comorbidity score

Other Asthma treatments and Asthma severity indicators	
Respiratory failure	LABA
Asthma exacerbation	SABA
Tuberculosis	SAMA
Lung Cancer	LAMA
Bronchiectasis	ICS (excluding Fluticasone)
Sarcoidosis	Omalizumab, Mepolizumab, Reslizumab, Benralizumab, Dupilumab
Pulmonary Hypertension	Leukotriene receptor antagonist (excluding Montelukast)
Interstitial lung disease, lung fibrosis, ARDS	Number of Pulmonologist visits
Acute Upper/ Lower Respiratory Tract infection	Pulmonary function test
Pneumonia	Antibiotics
Corticosteroids	

Comedication use	
Lithium	Diuretics
Anti-epileptic mood stabilizers	Nitrates
Anti-epileptics (other than mood stabilizers)	Lipid lowering drugs
Atypical antipsychotics	Non-insulin diabetes medications
Benzodiazepines	Insulin
Serotonin-norepinephrine reuptake Inhibitors	Antidepressants
Selective serotonin reuptake inhibitors	Angiotensin II receptor blockers (ARBs)
Tricyclic antidepressants (TCAs)	Angiotensin converting enzyme inhibitors (ACEi)
Typical antipsychotics	Calcium channel blockers
Anticoagulants	Beta blockers
Antiplatelet agents	Disease-modifying antirheumatic drugs (DMARDs)

DREAM study protocol - Comparison 10 Montelukast vs Fluticasone

Comorbid conditions	
Atrial fibrillation	Ischemic heart disease
Coronary artery disease	Chronic obstructive pulmonary disease
Heart failure	Malignancy
Stroke or transient ischemic attack	Drug or alcohol abuse or dependence
Peripheral vascular disease	Venous thromboembolism
Hyperlipidemia	Chronic liver disease
Renal dysfunction	Rheumatoid Arthritis

ICD-9, ICD-10, HCPCS, and NDC codes used to define the covariates listed above are available in Appendix A.

c. Outcome variables and study follow-up:

- **Primary outcome:** incident dementia, i.e., Alzheimer's disease, vascular dementia, senile, presenile, or unspecified dementia, or dementia in other diseases classified elsewhere. Outcome will be defined by 1 inpatient claim or 2 outpatient claims in analysis 1, 2, 3. In analysis 4, the outcome will be defined by 1 inpatient or 1 outpatient claims and 1 prescription claim for a symptomatic treatment [donepezil, galantamine, rivastigmine, and memantine] within 6 months of each other with outcome date assigned to second event in the sequence.
- Secondary outcomes: Individual component:
Alzheimer's disease

Condition	ICD-9 and ICD-10 codes
Alzheimer's disease	331.0*, F00*, G30*
Vascular dementia	290.4*, F01*
Senile, presenile, or unspecified dementia	290.0*, 290.1*. 290.3*, 797*, F03*
Dementia in other diseases classified elsewhere	331.1*, 331.2*, 331.7*, 294.1*, F02*

For analysis 1,3, and 4 the follow-up will start the day after initiation of Montelukast and Fluticasone and will continue until the earliest date of the following events:

- The first occurrence of the outcome of interest
- The date of end of continuous registration in the database,
- End of the study period,

DREAM study protocol - Comparison 10 Montelukast vs Fluticasone

- Measured death event occurs,
- The date of drug discontinuation, defined as the date of the last continuous treatment episode of the index drug (Montelukast and Fluticasone) plus a defined grace period (i.e., 90 days after the end of the last prescription's days' supply in main analyses).

For analysis 2, the follow-up will start 180 days after initiation of Montelukast and Fluticasone and will continue until the earliest date of the following events:

- The first occurrence of the outcome of interest, unless otherwise specified for selected outcomes,
- The date of end of continuous registration in the database,
- End of the study period,
- Measured death event occurs,
- Maximum allowed follow-up time (1095 days) reached

7. Propensity score analysis

We will use a propensity-score (PS)¹-based approach to account for measured confounding in this study. The PS will be calculated as the predicted probability of initiating the exposure of interest (i.e., the repurposing candidate) versus the reference drug conditional on baseline covariates using multivariable logistic regression constructed separately in each data source. On average, patients with similar PSs have similar distribution of potential confounders used to estimate the PS. Therefore, analyses conditioned on the PS provide effect estimates that are free from measured confounding. For all our analyses, initiators of each exposure of interest will be matched with initiators of the reference exposure based on their PS within each data source.² Pair matching will be conducted using a nearest-neighbor algorithm, which seeks to minimize the distance between propensity scores in each pair of treated and reference patients,³ and a caliper of 0.025 on the natural scale of the PS will be used to ensure similarity between the matched patients.⁴

We report multiple diagnostics for PS analysis in this protocol. First, the PS distributional overlap is provided between two groups before and after matching to ensure comparability of these groups.⁵ Next, balance in each individual covariate between two treatment groups is reported using standardized differences.⁶

8. Table for covariate balance

Variable	Unmatched			PS-Matched		
	Montelukast (N = 12,575)	Fluticasone (N = 38,958)	St. Diff	Montelukast (N = 12,572)	Fluticasone (N = 12,572)	St. Diff
Demographics						
Age, mean (SD)	72.8 (6.1)	73.3 (6.4)	-8.20	72.8 (6.1)	72.8 (6.1)	-0.30
Gender, n (%)						
Male	3694 (29.4)	12706 (32.6)	-7.00	3694 (29.4)	3764 (29.9)	-1.20
Female	8881 (70.6)	26252 (67.4)	7.00	8878 (70.6)	8808 (70.1)	1.20
Race, n (%)						
White	10614 (84.4)	33028 (84.8)	-1.00	10613 (84.4)	10650 (84.7)	-0.80
Black	831 (6.6)	3055 (7.8)	-4.80	831 (6.6)	881 (7)	-1.60
Hispanic	218 (1.7)	639 (1.6)	0.70	218 (1.7)	203 (1.6)	0.90
Other	912 (7.3)	2236 (5.7)	6.10	910 (7.2)	838 (6.7)	2.30
Region, n (%)						
Northeast; n (%)	2271 (18.1)	8670 (22.3)	#####	2271 (18.1)	2335 (18.6)	-1.30
South; n (%)	5310 (42.2)	13528 (34.7)	15.50	5307 (42.2)	5179 (41.2)	2.10
Midwest; n (%)	2498 (19.9)	8288 (21.3)	-3.50	2498 (19.9)	2546 (20.3)	-1.00
West; n (%)	2484 (19.8)	8431 (21.6)	-4.70	2484 (19.8)	2501 (19.9)	-0.30
Other; n (%)	12 (0.1)	41 (0.1)	-0.30	12 (0.1)	11 (0.1)	0.30
Calendar year of index date, n (%)						
2014	3143 (25)	10567 (27.1)	-4.90	3142 (25)	3037 (24.2)	1.90
2015	2585 (20.6)	8299 (21.3)	-1.80	2585 (20.6)	2519 (20)	1.30
2016	2396 (19.1)	7305 (18.8)	0.80	2394 (19)	2425 (19.3)	-0.60
2017	2330 (18.5)	6986 (17.9)	1.50	2330 (18.5)	2408 (19.2)	-1.60
2018	2121 (16.9)	5801 (14.9)	5.40	2121 (16.9)	2183 (17.4)	-1.30

DREAM study protocol - Comparison 10 Montelukast vs Fluticasone

Low income subsidy, n (%)	1824 (14.5)	6953 (17.8)	-9.10	1823 (14.5)	1859 (14.8)	-0.80
Dementia risk factors, n (%)						
Diabetes	4101 (32.6)	13257 (34)	-3.00	4098 (32.6)	4087 (32.5)	0.20
Obesity	2804 (22.3)	9138 (23.5)	-2.80	2804 (22.3)	2808 (22.3)	-0.10
Coronary artery disease	3338 (26.5)	11429 (29.3)	-6.20	3338 (26.6)	3264 (26)	1.30
Hypertension	9870 (78.5)	30962 (79.5)	-2.40	9867 (78.5)	9909 (78.8)	-0.80
Depression	2029 (16.1)	6989 (17.9)	-4.80	2029 (16.1)	2013 (16)	0.30
Anxiety	2235 (17.8)	6921 (17.8)	0.00	2235 (17.8)	2234 (17.8)	0.00
Bipolar disorder	126 (1)	555 (1.4)	-3.90	126 (1)	120 (1)	0.50
Schizophrenia	8 (0.1)	70 (0.2)	-3.30	8 (0.1)	3 (0)	1.90
Markers for healthy behavior, frailty, healthcare use						
Smoking, n (%)	2803 (22.3)	10651 (27.3)	#####	2803 (22.3)	2833 (22.5)	-0.60
Mammography, n (%)	4285 (34.1)	12152 (31.2)	6.20	4283 (34.1)	4262 (33.9)	0.40
Colonoscopy, n (%)	1465 (11.7)	4797 (12.3)	-2.00	1464 (11.6)	1465 (11.7)	0.00
Fecal occult blood test, n (%)	1172 (9.3)	3374 (8.7)	2.30	1172 (9.3)	1172 (9.3)	0.00
Influenza vaccination, n (%)	8417 (66.9)	26819 (68.8)	-4.10	8416 (66.9)	8463 (67.3)	-0.80
Herpes zoster vaccination, n (%)	3 (0)	11 (0)	-0.30	3 (0)	2 (0)	0.60
Pneumococcal vaccination, n (%)	5584 (44.4)	17347 (44.5)	-0.20	5583 (44.4)	5680 (45.2)	-1.60
Bone mineral density test, n (%)	1743 (13.9)	5139 (13.2)	2.00	1743 (13.9)	1732 (13.8)	0.30
Number of distinct prescriptions, mean (SD)	12.3 (5.8)	12.5 (5.8)	-2.30	12.3 (5.8)	12.2 (5.7)	2.00
Number of emergency room visits, mean (SD)	0.7 (1.4)	0.8 (1.6)	-8.80	0.7 (1.4)	0.7 (1.2)	1.20
Number of outpatient visits, mean (SD)	12.5 (8.4)	12.4 (8.6)	1.10	12.5 (8.4)	12.5 (8.6)	0.90
Number of hospitalizations, mean (SD)	0.2 (0.6)	0.2 (0.6)	-6.60	0.2 (0.6)	0.2 (0.5)	1.40

DREAM study protocol - Comparison 10 Montelukast vs Fluticasone

Number of C-reactive protein tests ordered, mean (SD)	0.2 (0.8)	0.2 (0.9)	-1.20	0.2 (0.8)	0.2 (0.8)	0.40
Number of serum creatinine tests ordered, mean (SD)	0.9 (1.6)	1.1 (2)	#####	0.9 (1.6)	0.9 (1.5)	1.60
Composite frailty score, mean (SD)	0.2 (0.1)	0.2 (0.1)	#####	0.2 (0.1)	0.2 (0.1)	1.40
Osteoporosis, n (%)	1911 (15.2)	5814 (14.9)	0.80	1911 (15.2)	1912 (15.2)	0.00
Fractures, n (%)	877 (7)	2787 (7.2)	-0.70	877 (7)	893 (7.1)	-0.50
Falls, n (%)	641 (5.1)	2326 (6)	-3.80	641 (5.1)	656 (5.2)	-0.50
Use of supplemental oxygen, n (%)	260 (2.1)	1091 (2.8)	-4.80	260 (2.1)	279 (2.2)	-1.00
Combined comorbidity score, mean (SD)	2.2 (2.2)	2.4 (2.4)	#####	2.2 (2.2)	2.2 (2.2)	0.50
Comedication use, n (%)						
Lithium	17 (0.1)	50 (0.1)	0.20	17 (0.1)	12 (0.1)	1.20
Anti-epileptic mood stabilizers	142 (1.1)	562 (1.4)	-2.80	142 (1.1)	149 (1.2)	-0.50
Anti-epileptics (other than mood stabilizers)	1839 (14.6)	6087 (15.6)	-2.80	1837 (14.6)	1778 (14.1)	1.30
Atypical antipsychotics	170 (1.4)	719 (1.8)	-3.90	170 (1.4)	158 (1.3)	0.80
Benzodiazepines	2537 (20.2)	7878 (20.2)	-0.10	2537 (20.2)	2523 (20.1)	0.30
Serotonin-norepinephrine reuptake inhibitors	715 (5.7)	2343 (6)	-1.40	715 (5.7)	721 (5.7)	-0.20
Selective serotonin reuptake inhibitors	2265 (18)	7367 (18.9)	-2.30	2265 (18)	2205 (17.5)	1.20
Tricyclic antidepressants (TCAs)	434 (3.5)	1548 (4)	-2.80	434 (3.5)	425 (3.4)	0.40
Typical antipsychotics	20 (0.2)	105 (0.3)	-2.40	20 (0.2)	24 (0.2)	-0.80
Anticoagulants	1163 (9.2)	4342 (11.1)	-6.30	1163 (9.3)	1217 (9.7)	-1.50
Antiplatelet agents	947 (7.5)	3416 (8.8)	-4.50	947 (7.5)	916 (7.3)	0.90
Nitrates	915 (7.3)	3131 (8)	-2.90	915 (7.3)	881 (7)	1.10
Lipid lowering drugs	6790 (54)	22232 (57.1)	-6.20	6789 (54)	6819 (54.2)	-0.50
Non-insulin diabetes medications	2391 (19)	7537 (19.3)	-0.80	2388 (19)	2415 (19.2)	-0.50

DREAM study protocol - Comparison 10 Montelukast vs Fluticasone

Insulin	725 (5.8)	2740 (7)	-5.20	725 (5.8)	705 (5.6)	0.70
Antidepressants	3634 (28.9)	11842 (30.4)	-3.30	3634 (28.9)	3557 (28.3)	1.40
Angiotensin converting enzyme inhibitors (ACEi)	3269 (26)	10938 (28.1)	-4.70	3268 (26)	3300 (26.2)	-0.60
Angiotensin II receptor blockers (ARBs)	3599 (28.6)	10554 (27.1)	3.40	3598 (28.6)	3563 (28.3)	0.60
Beta blockers	4312 (34.3)	14499 (37.2)	-6.10	4312 (34.3)	4274 (34)	0.60
Calcium channel blockers	3182 (25.3)	10328 (26.5)	-2.80	3181 (25.3)	3192 (25.4)	-0.20
Disease-modifying antirheumatic drugs (DMARDs)	457 (3.6)	1522 (3.9)	-1.40	457 (3.6)	452 (3.6)	0.20
Diuretics	5260 (41.8)	17028 (43.7)	-3.80	5259 (41.8)	5306 (42.2)	-0.80
Biologics (Omalizumab, Mepolizumab, Reslizumab, Benralizumab, Dupilumab)	89 (0.7)	218 (0.6)	1.90	89 (0.7)	77 (0.6)	1.20
Comorbid conditions, n (%)						
Atrial fibrillation	1527 (12.1)	5492 (14.1)	-5.80	1527 (12.1)	1543 (12.3)	-0.40
Heart failure	1397 (11.1)	5145 (13.2)	-6.40	1397 (11.1)	1352 (10.8)	1.10
Stroke or transient ischemic attack	858 (6.8)	3209 (8.2)	-5.40	858 (6.8)	867 (6.9)	-0.30
Peripheral vascular disease	1056 (8.4)	3915 (10)	-5.70	1055 (8.4)	1055 (8.4)	0.00
Hyperlipidemia	8900 (70.8)	27637 (70.9)	-0.40	8898 (70.8)	8820 (70.2)	1.40
Renal dysfunction	1706 (13.6)	6279 (16.1)	-7.20	1705 (13.6)	1704 (13.6)	0.00
Chronic liver disease	810 (6.4)	2628 (6.7)	-1.20	809 (6.4)	807 (6.4)	0.10
Ischemic heart disease	3250 (25.8)	11107 (28.5)	-6.00	3250 (25.9)	3170 (25.2)	1.50
Chronic obstructive pulmonary disease	5222 (41.5)	16890 (43.4)	-3.70	5220 (41.5)	5213 (41.5)	0.10
Malignancy	3369 (26.8)	11073 (28.4)	-3.70	3369 (26.8)	3411 (27.1)	-0.80
Drug or alcohol abuse or dependence	944 (7.5)	4336 (11.1)	#####	944 (7.5)	936 (7.4)	0.20
Venous thromboembolism	425 (3.4)	1565 (4)	-3.40	425 (3.4)	423 (3.4)	0.10
Rheumatoid Arthritis	595 (4.7)	1994 (5.1)	-1.80	595 (4.7)	592 (4.7)	0.10

DREAM study protocol - Comparison 10 Montelukast vs Fluticasone

Other Asthma treatments and Asthma severity indicators						
Asthma exacerbation, n (%)	213 (1.7)	478 (1.2)	3.90	211 (1.7)	174 (1.4)	2.40
Bronchiectasis, n (%)	347 (2.8)	1006 (2.6)	1.10	346 (2.8)	357 (2.8)	-0.50
Interstitial lung disease, lung fibrosis, ARDS, n (%)	1220 (9.7)	3941 (10.1)	-1.40	1219 (9.7)	1205 (9.6)	0.40
Lung Cancer, n (%)	144 (1.1)	674 (1.7)	-4.90	144 (1.1)	137 (1.1)	0.50
Pneumonia, n (%)	694 (5.5)	2455 (6.3)	-3.30	693 (5.5)	670 (5.3)	0.80
Pulmonary Hypertension, n (%)	194 (1.5)	691 (1.8)	-1.80	194 (1.5)	182 (1.4)	0.80
Respiratory failure, n (%)	723 (5.7)	2725 (7)	-5.10	722 (5.7)	704 (5.6)	0.60
Sarcoidosis, n (%)	60 (0.5)	259 (0.7)	-2.50	60 (0.5)	68 (0.5)	-0.90
Tuberculosis, n (%)	2157 (17.2)	7552 (19.4)	-5.80	2155 (17.1)	2177 (17.3)	-0.50
Acute Upper/ Lower Respiratory Tract infection, n (%)	4789 (38.1)	14315 (36.7)	2.80	4788 (38.1)	4850 (38.6)	-1.00
Pulmonary function test, n (%)	4989 (39.7)	13566 (34.8)	10.00	4988 (39.7)	4943 (39.3)	0.70
Number of Pulmonologist visits, mean (SD)	1.1 (2.4)	1 (2.5)	3.50	1.1 (2.4)	1.1 (2.5)	0.90
Antibiotics, n (%)	9638 (76.6)	29724 (76.3)	0.80	9636 (76.6)	9601 (76.4)	0.70
Corticosteroids, n (%)	6750 (53.7)	18540 (47.6)	12.20	6748 (53.7)	6551 (52.1)	3.10
ICS (excluding Fluticasone), n (%)	3647 (29)	8369 (21.5)	17.40	3644 (29)	3386 (26.9)	4.60
LAMA, n (%)	884 (7)	3315 (8.5)	-5.50	884 (7)	883 (7)	0.00
LABA, n (%)	2532 (20.1)	12953 (33.2)	#####	2532 (20.1)	2143 (17)	8.00
Leukotriene receptor antagonist (excluding Montelukast), n (%)	93 (0.7)	150 (0.4)	4.70	91 (0.7)	68 (0.5)	2.30
SABA, n (%)	6687 (53.2)	21764 (55.9)	-5.40	6684 (53.2)	6657 (53)	0.40
SAMA, n (%)	656 (5.2)	2193 (5.6)	-1.80	656 (5.2)	629 (5)	1.00

9. Statistical analysis plans

Incidence rates for the outcome will be estimated for the treatment and reference groups before and after PS matching. The competing risk of death could be of concern for the current set of analyses if mortality is frequent among patients included in the cohort and if differences in the risk of mortality between treatment and reference groups are substantial. In the PS-matched sample, we will use cause-specific hazard models⁷ to provide hazard ratios averaged over the entire follow-up period as well as interval specific hazard ratios (1, 2, and 3 years) for the association between the treatment of interest and risk of ADRD after considering all-cause mortality as a competing event. Pre-specified subgroup analyses will be conducted based on age, sex, and baseline cardiovascular disease.

10. References

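### Analysis 2 starts follow-up 180 days after initiation, but its dementia exclusion stops at the index date, so patients with a recorded diagnosis before time zero remain eligible

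*Combined protocol and SAP*

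**What the plan says.** Section 5b defines the index date once, for all analyses: "Day of initiation of new Montelukast versus Fluticasone use". It then gives two inclusion lists, one for analyses 1, 3 and 4 and one for analysis 2. The dementia criterion is the same in both: "No diagnosis of dementia any time prior to and including index date". The analysis 2 list adds one criterion that reaches past the index date: "180-day continuous use of Montelukast versus Fluticasone starting on the index date".

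The starts of follow-up differ. Under sections 5a and 6c, analyses 1, 3 and 4 start the day after initiation. For analysis 2, section 6c says: "For analysis 2, the follow-up will start 180 days after initiation of Montelukast and Fluticasone".

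The primary endpoint is incident dementia (sections 1b and 6c). On ascertainment, section 6c says: "Outcome will be defined by 1 inpatient claim or 2 outpatient claims in analysis 1, 2, 3". Analysis 2 follow-up ends at the earliest of several events, one of which is the first occurrence of the outcome. That entry allows exceptions for selected outcomes, but none is visible.

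**The concern.** In an analysis of incident disease, freedom from the disease should be established up to the moment the risk period opens. Analyses 1, 3 and 4 do this: the exclusion runs through the index date and risk time starts the next day. Analysis 2 moves the start of risk time by 180 days and leaves the exclusion where it was.

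Two things are at stake. First, patients who already carry a dementia code at time zero satisfy the written entry criteria, and some of them can later be counted as new cases. Second, the text does not settle what to do with them. Two programmers working from it could drop them, count them at the next claim or censor them, and would then have different risk sets and different matched samples.

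**Working it through.** The point is textual, so the check sets the sections side by side. Day 0 is the index date.

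**1. Can the index date in the analysis 2 list mean day 180?** No. The plan has one definition, the day of initiation, and the same list has 180 days of use beginning on that date.

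**2. Compare the windows.**

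| | Dementia exclusion ends | Follow-up starts | Days between |
|---|---|---|---|
| Analyses 1, 3, 4 | day 0 | day 1 | none |
| Analysis 2 | day 0 | day 180 | days 1 to 179 (180 − 1 = 179 days) |

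**3. Does another analysis 2 criterion cover the gap?** Age, enrollment, prior use, nursing home history and asthma claims are all assessed at or before the index date. The 180-day use criterion covers the gap but concerns drug use only.

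**4. Does the flowchart show a separate step?** The section 5c flowchart reproduces exactly:
- 23,466,175 − 21,749,739 = 1,716,436
- 1,716,436 − 1,010,844 = 705,592
- 705,592 − 113,159 = 592,433 (the dementia step)
- 592,433 − 62,588 = 529,845
- 529,845 − 454,167 = 75,678
- 75,678 − 24,145 = 51,533 = 12,575 + 38,958

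It has one dementia step. It has no row for 180-day use and none for a diagnosis between the index date and day 180. The analysis 2 cohort size is therefore not shown either.

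**5. Follow hypothetical patients, all still on drug at day 180.**

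| Patient | Meets the written entry criteria? | Meets the outcome definition before day 180? | Result |
|---|---|---|---|
| A: inpatient dementia claim on day 60 | yes | yes | Incident and first occurrence imply no time at risk; no eligibility text removes the patient |
| B: two outpatient claims, both before day 180 | yes | yes | As A |
| C: one outpatient claim on day 60, a second after day 180 | yes | no | The definition is completed during follow-up and can be counted as incident |
| D: one outpatient claim on day 60, none later | yes | no | Stays in the risk set with a recorded diagnosis |

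For A and B, the end of follow-up (first occurrence) falls before its start (day 180). The usual inference is that they contribute nothing, but it is only an inference. For C, that inference does not help, because one outpatient claim is not an occurrence of the outcome. Section 6c dates the outcome to the second event for analysis 4 only and gives no dating rule for the two-claim definition in analysis 2. By contrast, had C or D carried the same single code before the index date, the criterion would have barred them, since it refers to any diagnosis and not to the outcome definition.

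**6. Size.** A count would need the dementia rate, the analysis 2 cohort size, the share of gap diagnoses recorded as one outpatient code, and the share of those followed by a later claim. The documents give none of these.

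**The case against.** The strongest reply is that the plan already handles these patients. The endpoint is incident dementia and follow-up stops at the first occurrence, so someone who met the definition before day 180 cannot have a first occurrence afterwards. This stands for patients A and B. A reader might infer that every gap case is free to be counted as a new event, and the documents do not support that. They also do not support putting a percentage of events on the problem: a ratio of gap length to follow-up length would include the very patients whom the first-occurrence wording takes out.

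The reply does not reach patients C and D. It can be argued that C first meets the definition after day 180 and is properly incident. That is a defensible view of the outcome rule. It is not the standard the plan applies at entry, where any earlier diagnosis excludes.

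A second reply is that the study design diagrams in section 4, which are not visible in the text reviewed, may show an exclusion window running to the start of follow-up. They may. That would confirm the intention, and the written criterion, which ends at the index date, would still need to be brought into line with it.

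A third is that only one of four analyses is affected and that the visible text does not call it primary. This is correct and limits the weight of the point.

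**Conclusion.** The point holds as a mismatch between eligibility and time zero in analysis 2, and it should be fixed. Followed exactly, the written criteria admit patients with a dementia diagnosis recorded before follow-up starts. For those who fully meet the outcome definition by then, other wording implies that they have no time at risk, though the eligibility text leaves them in. For those with a single outpatient code in the gap, no visible text removes them, and a later claim can be counted as incident dementia.

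The size is unknown. Neither the number of patients nor the direction or amount of any bias in the hazard ratio follows from the documents. A reader might infer that the analysis 2 estimate is materially biased; nothing here shows that. The conclusion rests on the visible text and on reading the index date as the plan defines it. It does not touch analyses 1, 3 and 4.

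**What to change.** In the analysis 2 list, replace the dementia criterion with one requiring no dementia diagnosis at any time before the start of follow-up. Set the boundary so that no day is both excluded and at risk. Either exclude through day 179 and start follow-up on day 180, or exclude through day 180 and start on day 181. The second option repeats the pattern of analyses 1, 3 and 4 but also requires changing the start of follow-up in sections 5a and 6c.

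Apply the criterion before PS estimation and matching for analysis 2, because removing patients afterwards would break matched pairs. Report the number removed by arm, and align the text with the study design diagrams.

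The cost is a short text change, a re-run of analysis 2 only, and the loss of some patients with a single outpatient code in the gap, a few of whom might first have met the two-claim definition during follow-up. That loss is consistent with how the index-date rule already treats earlier single codes.

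### Prodromal cognitive decline is not directly controlled: no listed propensity-score covariate captures it, and no analysis excludes patients who show it

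*Combined protocol and SAP*

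**What the plan says.** Section 6b lists the baseline covariates. Under "Dementia risk factors" it gives diabetes, obesity, hypertension, coronary artery disease, depression, anxiety, bipolar disorder and schizophrenia. The other blocks cover demographics, health behaviour and frailty, asthma treatment and severity, comedication and comorbidity. None names a cognitive symptom, a pre-dementia diagnosis, Parkinson's disease, a cognitive work-up or an anti-dementia drug. The balance table in section 8 has no such row either. Covariate codes are referred to Appendix A, which was not available for this review.

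Section 5b sets two baseline exclusions that bear on cognition, in all four analyses: "No diagnosis of dementia any time prior to and including index date" and "No history of nursing home admission recorded in any time prior to and including index date".

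Section 7 says the propensity score is there to "account for measured confounding in this study". Section 6c separates the analyses. "For analysis 2, the follow-up will start 180 days after initiation of Montelukast and Fluticasone", and section 5b requires for it "180-day continuous use of Montelukast versus Fluticasone starting on the index date". Analyses 1, 3 and 4 start follow-up the day after initiation. Analysis 4 changes the outcome definition, using donepezil, galantamine, rivastigmine and memantine. The section 9 subgroups are age, sex and cardiovascular disease.

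**The concern.** The stated aim is dementia onset, and follow-up is short. A patient with recorded memory complaints, or already on donepezil without a dementia code, is eligible and can become an event soon after the index date. If such patients are unequally spread between the arms, the hazard ratio partly reflects who was already declining when treatment began. The balance table cannot reveal this, because no row measures it.

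The comparison sets a tablet against a drug that asthma patients inhale, so one can reason that a prescriber who notices early decline might favour one of them. That is a reason to measure the state at baseline. It is not evidence that such selection occurred.

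**Working it through.** **1. Is a direct marker present anywhere?** Read item by item:

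| Place | Bearing on pre-dementia cognition |
|---|---|
| Section 6b, all blocks | No cognitive item |
| Section 8 table | No cognitive row |
| Section 5b exclusions | Diagnosed dementia and nursing home admission, up to the index date |
| Analysis 2 | 180-day lag and 180-day continuous use; no cognitive criterion |
| Analysis 4 | Outcome definition only; the four symptomatic drugs are neither a baseline exclusion nor a covariate |
| Section 9 subgroups | None cognitive |

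The dementia exclusion in analysis 2 also ends at the index date, although follow-up begins at day 180.

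**2. Reproducing the plan's balance figures for nearby proxies.** Standardized difference = 100 × (p1 − p0) / √{[p1(1 − p1) + p0(1 − p0)] / 2}, from the section 8 counts. Denominators are 12,575 and 38,958 unmatched, and 12,572 per arm matched.

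| Covariate | Unmatched: stated / recomputed | Matched: stated / recomputed |
|---|---|---|
| Depression | −4.80 / −4.80 | 0.30 / 0.35 |
| Falls | −3.80 / −3.82 | −0.50 / −0.54 |
| Atypical antipsychotics | −3.90 / −3.94 | 0.80 / 0.84 |
| Stroke or TIA | −5.40 / −5.36 | −0.30 / −0.28 |

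The figures reproduce. These proxies were slightly commoner with fluticasone and are balanced after matching. The matched frailty score stands at 1.40.

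**3. How short is follow-up?** Take the matched index-year counts and assume mid-year entry and data to the end of 2018, so potential follow-up is 4.5, 3.5, 2.5, 1.5 and 0.5 years for 2014 to 2018.

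- Montelukast: (3142×4.5 + 2585×3.5 + 2394×2.5 + 2330×1.5 + 2121×0.5) / 12,572 = 33,727 / 12,572 = 2.7 years.
- Fluticasone: (3037×4.5 + 2519×3.5 + 2425×2.5 + 2408×1.5 + 2183×0.5) / 12,572 = 33,249 / 12,572 = 2.6 years.

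Censoring at discontinuation shortens this further in analyses 1, 3 and 4.

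**4. What could the omission do?** For an omitted binary state with hazard ratio R and prevalences p1 and p0 after matching, the bias factor is [1 + (R − 1)p1] / [1 + (R − 1)p0]. The documents give neither R nor prevalence. Assume R = 6 and p0 = 3%. A standardized difference d is then a prevalence gap of about (d/100) × √(0.03 × 0.97) = (d/100) × 0.1706, and the factor is about 1 + 5 × gap / 1.15.

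| Residual imbalance assumed | d | Gap | Factor |
|---|---|---|---|
| As matched depression | 0.3 | 0.0005 | 1.002 |
| As matched antipsychotics | 0.8 | 0.0014 | 1.006 |
| As matched frailty score | 1.4 | 0.0024 | 1.010 |
| As unmatched depression | 4.8 | 0.0082 | 1.036 |
| As unmatched stroke or TIA | 5.4 | 0.0092 | 1.040 |
| As unmatched heart failure | 6.4 | 0.0109 | 1.047 |

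As a cross-check, 3% against 2% is a standardized difference of 6.4 and gives 1.15 / 1.10 = 1.045. Reversing the imbalance gives the reciprocal.

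**5. Sensitivity to R.** At 3% against 2%, R = 3 gives 1.06 / 1.04 = 1.02 and R = 10 gives 1.27 / 1.18 = 1.08.

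**The case against.** The strongest reply is that the plan already limits this bias. Nursing home exclusion removed 62,588 people beyond the dementia exclusion. Both arms start an active treatment. The score matches on frailty, falls, fractures, depression, antipsychotics, stroke or TIA, comorbidity and healthcare use. Analysis 2 lags follow-up by 180 days. This stands, and it rules out calling early decline uncontrolled. It does not close the gap. The lag applies to one analysis, half a year need not outlast a slow decline, and balanced proxies do not establish balance in the state they stand in for.

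A reader might infer from the unmatched psychiatric differences that decline drives drug choice. The documents do not support that. The differences are small, with depression at −4.80 and bipolar disorder and atypical antipsychotics each at −3.90. They sit beside nulls (anxiety 0.00, benzodiazepines −0.10) and shrink to 0.80 or less after matching. The markers were commoner with fluticasone, the inhaled drug. Other inhaled corticosteroid use was higher with montelukast (29% against 21.5%), which fits poorly with avoidance of inhalers.

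A reader might also take larger bias factors as likely: 5% against 3% gives 1.25 / 1.15 = 1.09, and 6% against 3% gives 1.30 / 1.15 = 1.13. Those gaps are standardized differences of 10.2 and 14.5, whereas the largest matched value in the table is 8.00 (LABA). The documents offer no anchor for them. Nor do they show that the omitted markers are the strongest predictors of a dementia claim.

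The frailty or comorbidity score may contain cognitive or Parkinson's codes; without Appendix A this cannot be checked. Even so, a balanced composite does not show balance on a component. Finally, section 7 says "analyses conditioned on the PS provide effect estimates that are free from measured confounding". That is limited to measured confounding, so the omission is not an internal contradiction.

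**Conclusion.** The point holds as a gap in direct control. No listed covariate or balance row captures prodromal cognition, and no analysis excludes patients who show it, in a study of dementia onset with roughly 2.7 years of mean potential follow-up. Bias is plausible but not demonstrated, and its direction is unknown. With an assumed 6-fold hazard and about 3% prevalence, the factor is about 1.00 to 1.01 if residual imbalance resembles the matched proxies, and about 1.04 to 1.05 if it resembles the larger unmatched gaps, or the reciprocals if the imbalance runs the other way. Hazard and prevalence are assumptions, not figures from the documents. The change is worth making because it is cheap and settles the question either way.

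**What to change.** Add to the propensity score, from the baseline lookback: mild cognitive impairment, memory-loss and other cognitive-symptom codes, Parkinson's disease, counts of cognitive tests and neurology visits, and baseline use of donepezil, galantamine, rivastigmine or memantine. Report their standardized differences, unmatched and matched, in the section 8 table. Rerun analysis 1 as a sensitivity analysis excluding patients with any such baseline cognitive code or drug. State whether the composite frailty and comorbidity scores already contain cognitive or Parkinson's codes.

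The cost is extra code lists, a re-estimated score and rematch, and one further run on claims already held. The sensitivity analysis would lose what should be a small share of patients.
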